10.2. Study Monitoring

In accordance with ICH GCP guidelines, the study monitor must have access to the investigator's source documentation to verify the data recorded in the CRFs for consistency.

The monitor is responsible for routine review of the CRFs at regular intervals throughout the study to verify adherence to the protocol and the completeness, consistency, and accuracy of the data being entered on them. The monitor should have access to any subject records needed to

verify the entries on the CRFs. The investigator agrees to cooperate with the monitor to ensure that any problems detected during these monitoring visits are resolved.

10.2.1. Study Discontinuation

The Sponsor reserves the right to terminate the overall study at any time. The investigator reserves the right to discontinue the study at their institution at any time. Should this be necessary, both parties will arrange discontinuation procedures and notify the appropriate regulatory authority(ies), IRBs, and IECs. In terminating the study, the Sponsor and the investigator will assure that adequate consideration is given to the protection of the subjects' interests.

Appendix 2. Part A Schedule of Study Assessments for SAD Cohorts in Healthy Adult Subjects

Part A											
Study Stage	Inpatient ^a				Outpatient (Post-dose Follow-up Period)						
	Screening					W1	W2	W3	W4	W8	W12
Study Visit Week											
Study Visit Day±Visit Window	D -28 to -2	D -1	D1 ^b	D2	D3	D8±2	D15±2	D22±2	D29±2	D57±7	D85±7/ET
Informed consent	X										
Demography	X										
Medical history ^c	X										
Inclusion/exclusion criteria	X	X ^d									
Full physical examination ^e	X										X
Symptom-directed physical examination		X	X	X		X	X	X	X	X	
Alcohol assessment ^f		X				X	X	X	X	X	X
Body weight	X										
Height and BMI	X										
Vital signs ^g	X	X	X	X		X	X	X	X	X	X
Safety ECGs ^h	X		X	X		X					
Cardiodynamic ECG evaluation ⁱ			X	X							
Pregnancy test ^j	X	X							X	X	X
Screening viral serology ^k	X										
Laboratory assessments ^l	X		X	X	X	X	X	X	X	X	X
Urinalysis ^l	X		X	X							

Part A											
Study Stage	Inpatient ^a				Outpatient (Post-dose Follow-up Period)						
	Screening					W1	W2	W3	W4	W8	W12
Study Visit Week											
Study Visit Day±Visit Window	D -28 to -2	D -1	D1 ^b	D2	D3	D8±2	D15±2	D22±2	D29±2	D57±7	D85±7/ET
Urine for drugs of abuse ^m	X	X									
Randomization			X								
Study drug administration ⁿ			X								
Blood samples for PK analysis ^o			X	X	X	X					
Urine samples for PK analysis ^o			X		X	X					
Pooled urine ^o			X	X							
Review/record AEs ^p						X					
Concomitant medications						X					

AE = adverse event; BMI = body mass index; ECG = electrocardiogram; ET = End of Treatment; PK = pharmacokinetic; SAD = single ascending dose

Note: When scheduled at the same timepoints, the assessments of vital signs and 12-lead ECGs must be performed first, before the physical examinations, blood sample collections, and urine collections.

^a Subjects will be admitted to the clinical investigative site on Day -1 and discharged following the completion of the Day 2 assessments. If a subject discontinues prematurely, ET assessments should be performed.

^b Assessments performed predose unless otherwise specified.

^c Complete medical history will be taken at screening and any changes should be updated prior to dosing.

^d Evaluation of inclusion criteria related to urine pregnancy testing and urine drug screen.

^e See Section 7.2.1 for assessments to be performed during a full physical examination.

^f Subjects' alcohol intake will be recorded while on study.

^g Vital signs (blood pressure, pulse rate, respiratory rate and temperature) should be measured after the subject has rested comfortably for approximately 10 minutes. On Day 1, vital signs should be measured within 2 hours predose and 4 hours post-dose. On all other visit days, vital signs are only required to be recorded once during the visit.

^h 12-lead safety ECGs will be recorded on the timepoints listed in Appendix 4 and should be measured in the supine position after the subject has rested comfortably for 10 minutes.

ⁱ Replicate 12-lead ECGs will be extracted at the central ECG laboratory at timepoints shown in Appendix 4. Subjects must be resting supine for at least 10 minutes prior to and 5 minutes after each nominal timepoint.

^j WOCBP are required to have pregnancy tests. A blood pregnancy test will be performed at screening and urine pregnancy tests will be performed thereafter. Negative pregnancy test must be confirmed prior to study drug administration.

^k See Section 7.1.3 for viral serology parameters.

^l Clinical laboratory and urinalysis parameters are described in Section 7.2.8.

^m Drugs of abuse included in the screen are described in the inclusion/exclusion criteria. Screening results for drugs of abuse must be reviewed prior to dosing.

ⁿ Study drug will be administered via SC injection as described in Section 6.2.4.

^o Blood and urine samples for PK analysis will be collected at the timepoints listed in Appendix 4.

^p All AEs related to screening activities must be collected from the time of consent onwards; any other events occurring during the screening period should be reported as medical history. All SAEs must be collected from the time of consent onwards.

Appendix 3. Part B/C Schedule of Study Assessments for MAD Cohorts in Subjects with Chronic HBV Infection

Part B/C																
Study Stage	Screening	Dosing Period						Post-dose Follow-up Period ^b						Extended Follow-up Period ^c		
Study Visit Week				W1	W2	W3	W4 ^a	W5	W6	W7	W8	W12	W16	W20	W24	
Study Visit Day ± Visit Window	D -28 to -1	D1 ^a	D2	D8 ±2	D15 ±2	D22 ±2	D29 ^a ±2	D36 ±2	D43 ±2	D50 ±2	D57 ±2	D85 ±7	D113 ±7/ET	D141 ±7	D169 ±7	Q28D ±7
Informed consent	X															
Demography	X															
Medical history including HBV genotype ^d	X															
Inclusion/exclusion criteria	X	X ^c														
Full physical examination ^f	X						X						X			
Symptom-directed physical examination		X	X	X	X	X		X	X	X	X	X				
Alcohol intake assessment ^g		X		X	X	X	X	X	X	X	X	X	X	X	X	X
Body weight	X															
Height and BMI	X															
Vital signs ^h	X	X	X	X	X	X	X	X	X	X	X	X	X			
Safety ECG ⁱ	X	X	X				X									
Pregnancy test ^j	X	X					X				X	X	X			
FibroScan ^k	X															
Screening viral serology ^l	X															
Laboratory assessments ^m	X	X	X	X	X	X	X	X	X	X	X	X	X	X ⁿ	X ⁿ	X ⁿ
Urinalysis ^m	X	X														

Part B/C																
Study Stage	Screening	Dosing Period						Post-dose Follow-up Period ^b						Extended Follow-up Period ^c		
Study Visit Week				W1	W2	W3	W4 ^a	W5	W6	W7	W8	W12	W16	W20	W24	
Study Visit Day ± Visit Window	D -28 to -1	D1 ^a	D2	D8 ±2	D15 ±2	D22 ±2	D29 ^a ±2	D36 ±2	D43 ±2	D50 ±2	D57 ±2	D85 ±7	D113 ±7/ET	D141 ±7	D169 ±7	Q28D ±7
Urine for drugs of abuse ^o	X															
Randomization		X														
Study drug administration ^p		X					X									
Blood samples for PK analysis ^q		X	X	X			X ^r	X								
Blood sample for HBsAg	X	X	X	X	X	X	X	X	X	X	X	X	X	X	X	X
Blood sample for anti-HBs	X										X		X		X	X ^s
Blood sample for HBeAg qualitative	X															
Blood sample for HBeAg quantitative for Part C only ^t		X					X				X	X	X		X	X ^s
Blood sample for anti-HBe for Part C only	X										X		X		X	X ^s
Blood sample for HBV DNA quantitation ^u	X	X					X				X	X	X	X	X	X ^s
CCI																

Part B/C																
Study Stage	Screening	Dosing Period						Post-dose Follow-up Period ^b						Extended Follow-up Period ^c		
Study Visit Week				W1	W2	W3	W4 ^a	W5	W6	W7	W8	W12	W16	W20	W24	
Study Visit Day ± Visit Window	D -28 to -1	D1 ^a	D2	D8 ±2	D15 ±2	D22 ±2	D29 ^a ±2	D36 ±2	D43 ±2	D50 ±2	D57 ±2	D85 ±7	D113 ±7/ET	D141 ±7	D169 ±7	Q28D ±7
CCI																
Review/Record AEs ^x	X															
Concomitant Medications	X															
NUC medication adherence	X															

AE = adverse event; ECG = electrocardiogram; ET=end of treatment; **CCI** HBeAg = hepatitis e-antigen; HBsAg = hepatitis B surface antigen; HBV = Hepatitis B Virus; NUC = nucleoside/nucleotide; PK = pharmacokinetics; MAD = multiple ascending dose

Note: When scheduled at the same timepoints, the assessments of vital signs and 12-lead ECGs must be performed first, before the physical examinations, blood sample collections, and urine collections.

^a Assessments performed predose unless otherwise specified.

^b If a subject withdraws prematurely from the study prior to their Week 16 visit, ET assessments should be performed.

^c Additional HBsAg monitoring is required for subjects with HBsAg levels with a > 10% decrease from the Day 1 predose level at the Week 16 visit. Visits will occur every 4 weeks starting at Week 20 up to Week 48 or until the HBsAg level returns to ≥ 90% of the Day 1 predose level. For example, if Day 1 predose HBsAg is 560 IU/mL and Week 16 HBsAg is 490 IU/mL, the subject will be followed until HBsAg levels returns to ≥ 504 IU/mL. Additional HBsAg monitoring may be discontinued at the Sponsor’s discretion based on emerging data.

^d A complete medical history will be taken at screening including HBV genotype if available. Any changes should be updated prior to dosing.

^e Evaluation of inclusion criteria related to urine pregnancy testing and urine drug screen.

^f See Section 7.2.1 for assessments to be performed during a full physical examination.

^g Subjects’ alcohol intake will be recorded while on study.

^h Vital signs (blood pressure, pulse rate, respiratory rate, and temperature) should be measured in the supine position after the subject has rested comfortably for approximately 10 minutes. On Day 1, vital signs should be measured within 2 hours predose and 4 hours post-dose. On all other visit days, vital signs are only required to be recorded once during the visit.

ⁱ 12-lead safety ECGs will be recorded on the timepoints listed in Appendix 5 and should be measured in the supine position after the subject has rested comfortably for 10 minutes.

^j WOCBP are required to have pregnancy tests. A serum pregnancy test will be performed at screening and urine pregnancy tests will be performed thereafter. Negative pregnancy test must be confirmed prior to study drug administration.

^k Does not need to be performed if the subject has had a FibroScan in the 6 months prior to screening or liver biopsy in the year prior to screening that confirmed the absence of Metavir F3 fibrosis or F4 cirrhosis.

^l See Section 7.1.3 for viral serology parameters.

^m Clinical laboratory and urinalysis parameters are described in Section 7.2.8.

ⁿ Liver function tests only.

^o Drugs of abuse included in the screen are described in the inclusion/exclusion criteria. Screening results for drugs of abuse must be reviewed prior to dosing.

^p Study drug will be administered via SC injection as described in Section 6.2.4.

^q Blood samples for PK analysis will be collected at the timepoints listed in Appendix 5.

^r As a part of the Week 4 visit, subjects will return to the study center 24-hours after their initial post dose Week 4 PK sample is drawn to have a 24-hour post dose PK sample drawn.

^s Testing should occur again only at Week 36 and Week 48.

CCI

^u If a subject experiences ALT flare (as defined by ALT > 2x ULN) additional HBV DNA quantitation sample(s) may be collected

CCI

CCI

^x All AEs related to screening activities must be collected from the time of consent onwards; any other events occurring during the screening period should be reported as medical history. All SAEs must be collected from the time of consent onwards.

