2.2. Part B/C Objectives

The primary objective is:

- To evaluate the safety and tolerability of multiple doses of VIR-2218 in non-cirrhotic subjects with HBeAg-negative (Part B) and HBeAg-positive (Part C) chronic HBV infection on NUC therapy

The secondary objectives are:

- To characterize the PK of VIR-2218 in non-cirrhotic subjects with chronic HBV infection on NUC therapy
- To assess the antiviral activity of VIR-2218 in non-cirrhotic subjects with chronic HBV infection on NUC therapy

CCI

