Subjects enrolled in Part B/C of the study will remain outpatient. Subject screening will occur no more than 4 weeks prior to the Day 1 visit. Eligible subjects will undergo further assessments on Day 1 to qualify for study drug administration on Day 1. To exclude the presence of cirrhosis, screening will include a mandatory noninvasive assessment of liver fibrosis such as a FibroScan evaluation, unless the subject has results from a FibroScan evaluation performed within 6 months prior to screening or a liver biopsy performed within 1 year prior to screening that confirms the absence of Metavir F3 fibrosis or F4 cirrhosis.

Subjects in each cohort will be randomized 3:1 to receive VIR-2218 or placebo within 48 hours prior to study drug administration on Day 1. Subjects will return to the clinical investigative site at Week 4 to receive a second dose of the same study drug administered on Day 1. The decision to administer a second dose will be made based on Week 3 laboratory values in accordance with dose suspension/stopping criteria in Section 4.6.

CCI

Subjects will return to the clinical investigative site on an outpatient basis for safety, tolerability, PK, and antiviral activity monitoring at specified timepoints through the last Post-dose Follow-up Visit (Week 16). Additional HBsAg monitoring is required for subjects with HBsAg levels with a $> 10\%$ decrease from the Day 1 predose level at the Week 16 visit. Visits will occur

every 4 weeks starting at Week 20 up to Week 48 or until the HBsAg level returns to $\geq 90\%$ of the Day 1 predose level. Additional HBsAg monitoring may be discontinued at the Sponsor's discretion based on emerging data.

Based on review of the accumulated, available data in Parts A, B, and C, the SRC may recommend dosing of optional cohorts following the same stratification. In addition to the optional cohorts, a combined total of up to 16 "floater" subjects for Part B/C may be added to any cohort, as determined and approved by the SRC (see Section 4.5.5 and Appendix 6 for further information).

Fasting is not required for any study procedure/assessment. The assessments performed at each visit are described in Appendix 3 .

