Appendix 5. Part B/C Pharmacokinetic Assessment Timepoints

Study Day/Week	Protocol Time	PK Blood	Safety ECGs
Screening			X
Day 1	Predose	X ^a	X
	Dose		
	1 hour	X	
	2 hours	X	
	4 hours	X	X
	8 hours	X	X
Day 2	24 hours	X	X
Week 1		X	
Week 4	Predose	X ^a	X
	Dose		
	1 hour	X	
	2 hours	X	
	4 hours	X	X
	8 hours	X	
	24 hours	X	
Week 5		X	

^a At ≤ 15 minutes prior to dosing

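### Part B/C requires vital signs at 4 and about 24 hours after the first dose but none in the same period after the second; the first required reading after dose 2 is at Week 5.

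*Protocol*

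**What the plan says.** Protocol Section 4.1.2 makes Week 4 a dosing day: "Subjects will return to the clinical investigative site at Week 4 to receive a second dose of the same study drug administered on Day 1". Section 2.2 gives the Part B/C primary objective: "To evaluate the safety and tolerability of multiple doses of VIR-2218 in non-cirrhotic subjects with HBeAg-negative (Part B) and HBeAg-positive (Part C) chronic HBV infection".

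Appendix 3 sets the vital-signs timing through three footnotes:

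- Footnote h, on the vital-signs row: "On Day 1, vital signs should be measured within 2 hours predose and 4 hours post-dose", followed by "On all other visit days, vital signs are only required to be recorded once during the visit".
- Footnote a, attached to both the Day 1 and the Week 4 columns: "Assessments performed predose unless otherwise specified".
- Footnote r, on the Week 4 PK entry: "subjects will return to the study center 24-hours after their initial post dose Week 4 PK sample is drawn". The stated purpose is a 24-hour post-dose PK sample; no other assessment is named.

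The vital-signs row is marked at Screening, Day 1, Day 2, Weeks 1 to 8 and Weeks 12 and 16. Appendix 5 schedules PK samples at 1, 2, 4, 8 and 24 hours after the Week 4 dose, with a safety ECG before that dose and 4 hours after it.

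Section 7.2.4 describes how vital signs are taken but adds no time points. SAP Section 12.3.1 calculates change from baseline to the pre-dose assessment at each later visit and keeps unscheduled readings out of the summary tables.

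**The concern.** The two timing sentences in footnote h also appear, word for word, in Appendix 2, footnote g for Part A. There Day 1 is the only dosing day, so the rule covers all dosing. In Part B/C it covers one injection of two, and Week 4 becomes an ordinary visit day for vital signs.

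Part A is single-dose, so Part B/C is the study's only source of repeat-exposure data. Section 9.5 lists vital signs among the safety measures, and clinical assessments are a primary endpoint in Section 3.2. Under Section 4.5.3, escalation follows review of data that include the Week 6 visit. That review would cover the second dose without any required vital signs from its first 24 hours.

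**Working it through.** No power or error-rate figure is involved, and the plan states no number to reproduce. The check compares the two doses and counts days.

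**Required assessments after each dose (Appendices 3 and 5)**

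| Time after dose | Dose 1 (Day 1) | Dose 2 (Week 4, Day 29) |
|---|---|---|
| Predose | Vital signs | Vital signs (the single required reading, by footnotes h and a) |
| 4 hours | Vital signs, ECG, PK | ECG, PK |
| About 24 hours | Day 2: vital signs, symptom-directed examination, laboratory tests, ECG, PK | PK only (footnote r) |
| 1, 2, 3 weeks | Vital signs (Weeks 1, 2, 3) | Vital signs (Weeks 5, 6, 7) |
| Later | Week 4 predose | Vital signs (Weeks 8, 12, 16) |

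Required post-dose readings within about 24 hours: 2 after dose 1, 0 after dose 2. Required vital-sign visits after dose 2: 6 (Weeks 5, 6, 7, 8, 12 and 16).

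**Does another reading of the footnotes close the gap?** Footnote r treats the 24-hour return as part of the Week 4 visit, so a site might take its one reading then. Footnote a points to predose instead, and SAP Section 12.3.1 also works from the pre-dose value. Even if the reading were taken after the injection, there would be only one required reading for that visit, with no predose partner.

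**Time from dose 2 to the next required reading**

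- Nominal: Day 36 − Day 29 = 7 days.
- Week 4 window, Day 29 ± 2: Days 27 to 31. Week 5 window, Day 36 ± 2: Days 34 to 38.
- Shortest gap: 34 − 31 = 3 days. Longest gap: 38 − 27 = 11 days.

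**Subjects affected (if all receive dose 2)**

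- Planned: 3 Part B cohorts + 1 Part C cohort = 4 cohorts; 4 × 4 = 16 subjects, of whom 4 × 3 = 12 are active.
- Maximum in Section 5.1: 20 + 12 + 16 floaters = 48; at 3:1, 48 × 3/4 = 36 active.

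**The case against.** The strongest reply is that the second-dose schedule is lighter by design. Appendix 5 also reduces the ECGs, from 4, 8 and 24 hours after dose 1 to 4 hours after dose 2. The authors plainly recognised Week 4 as a dosing day, since footnote a is attached to it and a full physical examination is scheduled there. Part A subjects given at least the same cumulative dose in one administration have 4-hour and Day 2 vital signs, and Section 4.5.3 requires their Week 4 data to be reviewed first. Some dose-selection and risk text is redacted, so a rationale may exist that cannot be seen.

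Part of this stands. The lighter schedule could be deliberate, and carry-over from Part A is an inference. But the ECG reduction kept the 4-hour time point, so it does not explain dropping vital signs at the same moment. Part A addresses the size of the exposure, not re-exposure. Site burden is not a reason either, because the subject is present for the 4-hour ECG and PK sample.

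A reader might also infer that Part B/C collects no vital signs after repeat exposure, that the two doses cannot be compared at all, or that an acute reaction would go undetected. The documents do not support any of these. Six later visits have vital signs, and Weeks 1 to 3 after dose 1 pair with Weeks 5 to 7. Section 8.3 collects all adverse events once study drug has started, Section 7.1 allows unscheduled safety visits, the cohort stopping rules in Section 4.6.1 run on adverse events, and footnote h sets a minimum rather than a ceiling. What these safeguards leave open is narrower. Section 8.1.3 makes an abnormal vital sign a required adverse event when it comes with signs or symptoms, so a transient change without symptoms may not be measured. Extra readings taken at unscheduled assessments would generally reach the SAP listings but not its summary tables.

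**Conclusion.** The concern holds in a limited form. No vital signs are required after the injection on the day of dose 2 or at the 24-hour return, whereas both readings are required after dose 1. The first required reading after dose 2 is nominally 7 days later, with a range of 3 to 11 days.

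The loss is systematic measurement of acute, mainly asymptomatic, vital-sign change after repeat exposure, together with the 4-hour and 24-hour comparison of the two doses. It applies to each subject given a second dose: 16 planned (12 active), at most 48 (36 active). The conclusion rests on reading Week 4 as one of the other visit days in footnote h, and on no unseen manual adding a reading. It does not threaten the study, but it leaves an avoidable gap in data for the primary objective and is cheap to improve.

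**What to change.** Reconcile Appendix 3 footnotes a and h with the two dosing days, the Week 4 4-hour ECG in Appendix 5 and the multiple-dose objective. The simplest way is to reword footnote h so that the existing Day 1 predose and 4-hour post-dose vital-signs timing applies to each dosing day, Day 1 and Week 4. This restores the 4-hour comparison. The 24-hour comparison would also need vital signs at the PK return that is already scheduled, which is optional.

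The SAP needs a matching line. Section 12.3.1 gives a post-dose reading no stated place in the change calculation, and that includes the Day 1 4-hour reading already collected. Add that post-dose readings on both dosing days are summarised as change from the predose value of the same day.

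The cost is one extra reading and one eCRF time point per subject at a visit already attended, plus a short SAP addition. If second doses have already been given, state the gap as a limitation in the clinical study report; the SAP line is still useful for the Day 1 readings.

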Appendix 4. Part A Pharmacokinetic Assessment Timepoints

Study Day/Week	Protocol Time	PK Blood	Urine PK	Pooled Urine	Cardiodynamic Extracted ECGs	Safety ECGs
Screening						X
Day 1	Predose	X ^a	X ^a		X ^b	X
	Dose			X 0-4 hours		
	30 min	X			X	
	1 hour	X			X	X
	2 hours	X			X	
	4 hours	X		X 4-8 hours	X	X
	6 hours	X			X	
	8 hours	X		X 8-12 hours	X	X
	10 hours	X			X	
	12 hours	X		X 12-24 hours	X	
Day 2	24 hours	X			X	X
Day 3	48 hours	X	X			
Week 1		X	X			X

^a At ≤ 15 minutes prior to dosing

[figure not shown]
^b At 3 timepoints (-45, -30 and -15 minutes) prior to dosing

Appendix 5. Part B/C Pharmacokinetic Assessment Timepoints

Study Day/Week	Protocol Time	PK Blood	Safety ECGs
Screening			X
Day 1	Predose	X ^a	X
	Dose		
	1 hour	X	
	2 hours	X	
	4 hours	X	X
	8 hours	X	X
Day 2	24 hours	X	X
Week 1		X	
Week 4	Predose	X ^a	X
	Dose		
	1 hour	X	
	2 hours	X	
	4 hours	X	X
	8 hours	X	
	24 hours	X	
Week 5		X	

^a At ≤ 15 minutes prior to dosing

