9.2 Plasma PK Parameters

Pharmacokinetic analysis will be performed on the plasma PK concentration data to determine PK parameters by non-compartmental analysis using Phoenix WinNonlin® software (version 8.1 or higher).

Actual sampling times will be used for the PK analysis and if the actual sampling time is not recorded, the nominal sampling time will be used.

PK parameters (applicable for single dose cohorts in part A, day 1-dose and day-29 dose of multiple dose cohorts in part B and C):

Due to the short plasma half-life of VIR-2218 and metabolite, pharmacokinetic analysis will be performed separately for day-1 dose and day-29 dose in patients in parts B/C.

The following PK parameters of VIR-2218 and its metabolites to be determined at defined timepoints include:

- **C_{max}** : Individual maximum concentration (C_{max}) values are directly determined from the plasma concentration time profiles for each subject.
- **t_{max}** : The time to attain C_{max} . If the same C_{max} concentration occurs at different time points, t_{max} is assigned to the first occurrence of C_{max} .
- **t_{last}** : Time of last measurable (positive) observed concentration

- **C_{last}**: Observed concentration corresponding to t_{last}.
- **AUC_{0-t}**: The areas under the curve spanning time interval from 0 to t (up to the last time point with measurable concentration). AUC_{0-t} will be calculated using the linear-up /logarithmic-down trapezoidal rule.

Linear trapezoidal rule:

The area of the trapezoid between the two data points (t₁, C₁) and (t₂, C₂) where C₂ ≥ C₁ will be computed by:

$$AUC_{t_1-t_2} = 0.5(t_2 - t_1)(C_1 + C_2)$$

Logarithmic trapezoidal rule:

The area of the trapezoid between the two data points (t₁, C₁) and (t₂, C₂) where C₂ < C₁ will be computed by:

$$AUC_{t_1-t_2} = \frac{((t_2 - t_1)(C_1 - C_2))}{\ln C_1 - \ln C_2}$$

- **AUC_{0-12hr}**: The area under the plasma concentration-time curve over the time interval from 0 to 12 hr using the linear-up /logarithmic-down trapezoidal rule.
- **AUC_{0-24hr}**: The area under the plasma concentration-time curve over the time interval from 0 to 24 hr using the linear-up /logarithmic-down trapezoidal rule.
- **AUC_{0-∞}**: The area under the plasma concentration-time curve over the time interval from 0 extrapolated to infinity will be calculated according to the following equation:

$$AUC_{0-\infty} = AUC_{0-t} + \frac{C'_t}{\lambda_z}$$

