where C'_t is the predicted concentration at the time t (last time point with a measurable plasma concentration above the quantification limit) at which quantification was still possible, the calculation of λ_z is given below.

- **AUC_{%extrap}**: The percentage of the AUC that has been extrapolated beyond the last observed data point, calculated as:

$$AUC_{\%extrap} = \left(\frac{AUC_{0-\infty} - AUC_{0-t}}{AUC_{0-\infty}} \right) * 100$$

- **λ_z**: The apparent terminal rate constant λ_z will be estimated from a regression of ln(C) versus time over the terminal log-linear drug disposition portion of the concentration-time profiles. To calculate the elimination rate constant, the terminal data from a concentration-time curve will be used. Starting with the final non-BLQ data point and moving backwards, toward time zero, at least 3 data points not included C_{max} are fit to a linear regression. The number of data points used can be determined by maximizing the value adjusted-r² which defines the “best-fit” of the data.

The first order rate constant associated with the terminal (log-linear) portion of the curve will be estimated via linear regression of time vs. log concentration. The rules are that a minimum of three points is needed to define the terminal (log-linear) portion of the

curve, λ_z must be positive, and the selection is based on the best adjusted

square coefficient of regression (r^2). Additionally, if the adjusted r^2 does not improve, but is within 0.0001 of the largest adjusted R^2 value, the regression with the larger number of points is used.

The “adjusted” r^2 is calculated using the following equation:

$$\bullet \quad Adjusted\ r^2 = 1 - (1 - r^2) * \frac{(n-1)}{(n-2)},$$

where n = the number of data points used in the regression.

The slope of the line is equal to $-\lambda_z$ (i.e., the slope will be negative, but λ_z is a positive value).

If terminal concentration-time point(s) increases, this time point may be included if the $t_{1/2}$ estimate is reasonable. If λ_z is not determinable (for example, adjusted- r^2 value <0.8) then consequently only parameters not requiring λ_z will be reported. In addition, the lower (R_{start}) and upper (R_{end}) limit on time (h) for values to be included in the calculation of λ_z will be listed.

- **$t_{1/2}$:** The terminal half-life will be calculated from the terminal rate constant using the equation:

$$T_{1/2} = \frac{Ln(2)}{\lambda}$$

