- **CL/F:** The total clearance will be calculated as following:

$$CL/F = \frac{D}{AUC_{0-\infty}}$$

where D is dose.

- **V_z/F:** The apparent volume of distribution based on terminal phase will be calculated according to the following equation:

$$V_z/F = \frac{CL/F}{\lambda_z}$$

Other important PK considerations

- The value of $AUC\%_{extrap}$ will be less than or equal to 20% for the $AUC_{0-\infty}$ to be considered well estimated. If this proportion is > 20%, then the values of $AUC_{0-\infty}$ will be treated with caution, and emphasis will be placed on AUC_{0-t} values (i.e. in subsequent statistical analyses).
- If $AUC\%_{extrap} > 20\%$, all elimination related parameters (λ_z , $AUC_{0-\infty}$, $t_{1/2}$, CL/F or CL/F_{ss} , and V_z/F or V_z/F_{ss}) will be presented in the listings but excluded from the calculation of summary statistics. All values excluded from the summaries should be flagged in the individual listings with an explanation for the exclusion.
- If data permits, the other PK parameters may be reported.
- If $t_{last} = t_{max}$, C_{max} will not be reported for that subject in the listings. It will be footnoted to indicate that sampling timepoints were not appropriate for that subject.
- If $t_{last} < 24hr$, AUC_{0-24hr} will only be reported when $AUC\%_{extrap} < 20\%$; It will be presented in the listing with footnote to indicate that AUC_{0-24hr} was extrapolated. In the summary

tables, the cohort will be footnoted to indicate that subjects with extrapolated AUC_{0-24hr} were included in the calculation of summary statistics.

- If $t_{last} < 12hr$, AUC_{0-12hr} will only be reported when $AUC\%_{extrap} < 20\%$; It will be presented in the listing with footnote to indicate that AUC_{0-12hr} was extrapolated. In the summary tables, the cohort will be footnoted to indicate that subjects with extrapolated AUC_{0-12hr} were included in the calculation of summary statistics.

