9.6 DOSE PROPORTIONALITY FOR PK PARAMETERS

Dose proportionality will be evaluated separately for healthy subjects (part A) and day-1 dose of CHB subjects (part B and C) based on subjects without dosing deviations.

To assess dose proportionality, the natural log transformed, dose normalized $AUC_{0-\infty}$, AUC_{0-t} , AUC_{0-12} , AUC_{0-24} and C_{max} parameters will be evaluated using power model [2], with VIR-2218 dose level as the independent variable.

The power model for assessment of dose proportionality has the form of $\log(y) = \log(\beta_0) + \beta_1 \log(Dose)$ where y represents the PK parameter of interest. Dose proportionality is concluded if 90% CI for the β_1 falls within 0.7 to 1.43, which is less than 30% difference between doses for a given PK parameter.

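### Part B/C draws no plasma between 8 and 24 h, so its AUC0-12 is always interpolated or extrapolated, and with a BLQ 24 h sample it can be reported only if tmax is 1 h

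*Protocol*

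**What the plan says.** **Sampling.** Under "Appendix 4. Part A Pharmacokinetic Assessment Timepoints", plasma is drawn at 0.5, 1, 2, 4, 6, 8, 10, 12, 24 and 48 h and at Week 1. Under "Appendix 5. Part B/C Pharmacokinetic Assessment Timepoints", the post-dose draws are at 1, 2, 4, 8 and 24 h for both doses, followed by Week 1 or Week 5.

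**Parameter.** SAP 9.2 (Plasma PK Parameters) defines AUC0-12 as "The area under the plasma concentration-time curve over the time interval from 0 to 12 hr using the linear-up /logarithmic-down trapezoidal rule". It describes its parameter list as "applicable for single dose cohorts in part A, day 1-dose and day-29 dose of multiple dose cohorts in part B and C".

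**Reporting rules.** SAP 9.1 treats BLQ values after the first quantifiable one as missing. In SAP 9.2, lambda-z needs "at least 3 data points not included" Cmax, and an adjusted r² below 0.8 is given as an example of lambda-z not being determinable. If t_last is under 12 h, AUC0-12 is reported only when AUC%extrap is below 20%. A parallel rule covers AUC0-24 when t_last is under 24 h. For extrapolated values the SAP adds: "In the summary tables, the cohort will be footnoted to indicate that subjects with extrapolated" values were included.

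**Use.** SAP 9.6 states: "Dose proportionality will be evaluated separately for healthy subjects (part A) and day-1 dose of CHB subjects (part B and C"). AUC0-12 is one of five parameters in the power model. Proportionality is concluded if the 90% CI for the slope lies within 0.7 to 1.43.

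**The concern.** The 12 h endpoint fits the Part A schedule and appears to have been carried over to Part B/C, where no sample supports it.

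Two things are at stake in the Part B/C power model. First, subjects may leave the AUC0-12 regression because their 24 h sample is BLQ. Under dose-proportional kinetics that is more likely at lower doses, so the regression could lose the low end of its dose range. SAP 3.6 lists Part B groups down to 20 mg, and a cohort has only 3 active subjects before any floaters. Second, among subjects whose last measurable sample is at 8 h, only those peaking at 1 h can stay, which selects on speed of absorption.

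A smaller matter is that the SAP's footnote covers only values with t_last under 12 h. An AUC0-12 interpolated across the 16 h gap is not flagged.

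**Working it through.** The plan gives no figure to reproduce here; no formal sample size calculation was made.

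**1. Count of lambda-z points (documents only).** Assume the 24 h sample and the following weekly sample are BLQ, so t_last is at most 8 h. Points after Cmax on the 1, 2, 4, 8 h grid:

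| t_last | tmax 1 h | tmax 2 h | tmax 4 h | tmax 8 h |
|---|---|---|---|---|
| 8 h | 3 | 2 | 1 | 0 |
| 4 h | 2 | 1 | 0 | – |

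Three are needed. Only t_last = 8 h with tmax = 1 h qualifies, with no point to spare. Even then the fit and the 20% limit must be met. In every other cell there is no lambda-z, so no AUC%extrap and no AUC0-12.

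**2. AUC0-24.** A BLQ 24 h sample puts t_last below both 12 and 24 h, so AUC0-24 meets the same condition. A quantifiable sample at nominal 24 h triggers neither rule. The common cause is the 8 to 24 h gap.

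**3. How much could be lost (assumed inputs).** SAP 9.2 says only that the plasma half-life is short. A one-compartment subcutaneous model with dose-proportional kinetics was simulated on the Appendix 5 times under the SAP rules. Assumed half-lives were 2, 3, 4 and 6 h, absorption rates (ka) 0.5 and 2 per h, and ratios of median 50 mg peak to LLOQ from 3 to 1000 (5 values), giving 4 × 2 × 5 = 40 combinations. Percentage of subjects with a reportable AUC0-12 at 20/50/100/200 mg:

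| Half-life, ka, ratio | Part B/C schedule | Part A schedule |
|---|---|---|
| 2 h, 0.5, 3 | 0/0/0/3 | 0/17/74/98 |
| 3 h, 0.5, 10 | 0/3/13/34 | 61/99/100/100 |
| 4 h, 0.5, 10 | 2/15/43/72 | 77/100/100/100 |
| 4 h, 2, 30 | 21/43/70/87 | 100/100/100/100 |
| 6 h, 2, 10 | 3/38/72/92 | 69/100/100/100 |
| 6 h, either ka, 1000 | 100/100/100/100 | 100/100/100/100 |

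In none of the 40 combinations did the Part B/C share fall as dose rose.

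**4. Effect on the power-model slope (stylised).** Take 3 active subjects in each SAP 3.6 group: Part B 20, 50, 100, 200 mg; Part C 50, 200 mg. SE(slope) = σ/√Sxx, where Sxx is the sum of squared deviations of ln(dose). Assume a log-scale residual SD σ = 0.3, and that whole dose levels are lost while the others stay complete.

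| Doses kept | n | Sxx | SE | 90% half-width |
|---|---|---|---|---|
| all | 18 | 12.24 | 0.086 | 1.746 × 0.086 = 0.15 |
| without 20 mg | 15 | 5.77 | 0.125 | 1.771 × 0.125 = 0.22 |
| without 20 and 50 mg | 9 | 0.961 | 0.306 | 1.895 × 0.306 = 0.58 |

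The SE rises by √(12.24/5.77) = 1.46 and √(12.24/0.961) = 3.57. The acceptance range has half-width (1.43 − 0.7)/2 = 0.365, so in the last row the CI cannot fit at σ = 0.3. It could fit only if σ were below 0.365 × √0.961/1.895 = 0.19.

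**5. When the 24 h sample is quantifiable.** In three two-phase test curves, log-down interpolation gave AUC0-12 a bias of −1.5% to −4.2%, against −2.0% to −2.4% with Part A sampling.

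**6. What AUC0-8 covers.** For a one-compartment profile, AUC0-8/AUC0-12 = g(8)/g(12), where g(T) = (1 − e^(−ke·T))/ke − (1 − e^(−ka·T))/ka. Half-life 2 h with absorption half-life 0.5 h (ke = 0.347, ka = 1.386) gives 1.98/2.12 = 94%. Half-life 10 h with absorption half-life 3 h (ke = 0.0693, ka = 0.231) gives 2.49/4.09 = 61%. Over 112 combinations (half-life 2 to 10 h, absorption half-life 0.5 to 3 h, LLOQ 2 to 20% of the 50 mg peak), the 8 h sample is BLQ at 50 mg in 1. At 20 mg it is BLQ in 9 to 11, depending on the exact grid values.

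**The case against.** A reader might infer that AUC0-12 will go missing mainly in the low-dose cohorts. The documents do not support that as a fact. It needs an LLOQ, a half-life and a tmax, none of which they give. The simulated range includes no loss at any dose and near-total loss at every dose. Only the direction of a partial loss follows, and only under dose-proportional kinetics.

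A reader might also infer that Part B/C has no usable AUC0-12, or that the 12 h endpoint alone is at fault. Neither holds. A quantifiable 24 h sample gives AUC0-12 by the SAP's own log-down rule, with small error in the curves tested. AUC0-24, in the same model, is lost under the same condition.

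Two further defences have weight. AUC0-t and Cmax need no lambda-z and are both in the power model, and SAP 9.2 directs emphasis to AUC0-t when extrapolation exceeds 20%. But AUC0-t would end at 8 h in some subjects and 24 h in others, so it is not a fixed-interval measure. Also, the secondary endpoints name AUC to the last measurable time and to infinity, not AUC0-12, and SAP 3.3 plans no formal hypothesis testing. That limits the severity but does not remove the mismatch.

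**Conclusion.** The mismatch between SAP 9.2/9.6 and Appendix 5 stands on the documents alone, as does the result that a BLQ 24 h sample leaves AUC0-12 unreportable unless tmax is 1 h. This uses the SAP's BLQ rule; protocol 9.3.2 instead sets post-dose BLQ values to half the LLOQ.

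How often this happens is unknown. The simulated losses and the slope precision rest on assumed kinetics, LLOQ and residual SD, and losing whole dose groups is a bounding case. The sponsor, who knows the assay limit, can settle the question quickly.

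Severity is minor to moderate: a supplementary parameter in a descriptive analysis, but one for which the SAP sets a formal-looking criterion. This is a cheap improvement.

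**What to change.** In SAP 9.2 and 9.6:

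- For Part B/C, replace AUC0-12 with AUC0-8 as the fixed-interval partial AUC (Day 1 and Day 29; Day 1 in the power model).
- Compute AUC0-8 in Part A too, where an 8 h sample exists, so that both populations share one partial AUC ending at a scheduled draw. Keep AUC0-12 for Part A.
- Because the SAP uses actual sampling times, say how a nominal 8 h draw taken slightly early closes the interval.
- Report by dose group how many Part B/C subjects lack AUC0-24, and interpret its power-model slope in that light. Changing AUC0-12 does not cure AUC0-24.

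The cost is SAP wording, one more partial-area setting in the non-compartmental run and one count table; no sampling changes. The downside is that AUC0-8 covers less of the exposure (61% to 94% of AUC0-12 in the assumed profiles above). It may also still be missing in some subjects at the lowest dose if the 8 h sample is BLQ.
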